14.1	Data Management Responsibilities	46
14.2	Data Capture Methods.....	46
14.3	Types of Data.....	47
14.4	Timing/Reports.....	47
14.5	Study Records Retention	47
14.6	Protocol Violations/ Reportable Events.....	47
15	Publication Policy.....	49
16	Literature References	50
17	APPENDICES.....	52

LIST OF ABBREVIATIONS

ACASI	Audio Computer Assisted Survey Interview
AE	Adverse Event
AI	American Indian
AI/AN	American Indian/Alaska Native
BRFQ	Basic Research Factors Questionnaire (referred as ACASI survey)
CHRs	Community Health Representatives
CNOHR	Center for Native Oral Health Research
COHS	Community Oral Health Specialist
COMIRB	Colorado Multiple Institutional Review Board
CTCAE	Common Terminology Criteria for Adverse Events
dmfs	Decayed, missing and filled tooth surfaces index (primary)
DSMB	Data and Safety Monitoring Board
ECC	Early Childhood Caries
FV	Fluoride Varnish
HIPAA	Health Information Portability and Accountability Act
HRSA	Health Resources and Services Administration
HS	Head Start
HSCs	Head Start Centers
IHS	Indian Health Service
MAR	Missing at Random
MCAR	Missing Completely at Random
MNAR	Missing Not at Random
MOP	Manual of Procedures
NHANES	National Health and Nutrition Examination Survey
NIDCR	National Institute of Dental and Craniofacial Research
NN	Navajo Nation
NNHRRB	Navajo Nation Human Research Review Board
OHP	Oral Health Promotion
PI	Principal Investigator
RDHs	Registered Dental Hygienists
SA	Specific Aim
SAE	Serious Adverse Event
SODM	School of Dental Medicine
UCD	University of Colorado Anschutz Medical Campus
UP	Unanticipated Problems

PROTOCOL SUMMARY

Title:	Preventing Caries in Preschoolers: Testing a Unique Service Delivery Model in American Indian Head Start Programs
Phase:	IV
Population:	Children ages 3-6 years in Head Start (HS) Programs in the Navajo Nation (NN)
Number of Sites:	3 (Navajo Nation, University of Colorado Anschutz Medical Campus, University of California San Francisco)
Study Duration:	The study duration will be 6 years. This includes 1 year for planning, 6 months for each intervention year (1 & 2) for recruitment, 3 years for implementation of the interventions: baseline and follow-up evaluations, and 1 year for close-out and analysis.
Subject Participation Duration:	Each participant will be in the study for up to 3 years; 2 years of intervention and a third year for follow up measures.
Description of Agent or Intervention:	Intervention will include application of fluoride varnish (FV) offered offered 4x a year and oral health promotion (OHP) and education for 2 years.
Objectives:	
Primary:
 
1) To develop, with input from tribal/community members, a manualized intervention protocol for an early childhood caries (ECC) prevention program to be delivered by specially trained community paraprofessionals, called Community Oral Health Specialists (COHS)2) To implement and evaluate the delivery of FV and OHP programs in American Indian (AI) Head Start Centers (HSCs) under the following conditions: Group #1—FV offered 4x a year and OHP for 2 years provided by COHS Group #2— Usual oral health care made available by the IHS Dental providers (or other usual providers)3) To assess efficacy by comparing decayed, missing, and filled

primary tooth surfaces (dmfs) over time between the 2 groups.

Secondary:

- 1) To assess specific caries patterns
- 2) To investigate moderators/mediators of the intervention conditions as ascertained via questionnaires on oral health knowledge, attitudes, and behaviors
- 3) To investigate participant utilization of medical and dental services for oral health problems and intervention costs, intervention savings, net intervention costs, costs/net costs per participant, costs/net costs per unit decrease in caries associated with each intervention condition

[figure not shown]
**Description of Study
Design:**

The study design will be a cluster randomized design. HSCs within the Navajo Nation (NN) will be stratified by population size and randomized within strata to the two groups. All children within the HSC classrooms and a parent/primary caregiver of each child will be invited to participate in the intervention condition to which the HSC is randomized. Children will participate after informed consent by the parents and after informed consent by the participating parent/primary caregiver for her/himself. To be consistent with NIDCR, we will count the child and participating parent/primary caregiver dyad as one enrolled participant (unit). Baseline and annual measures of dmfs and of dental knowledge, attitudes, and behavior will be collected. Changes in these outcome measures will be compared between the two groups.

**Estimated Time to
Complete Enrollment:**

6 months for each intervention year (year 1 and year 2)

Schematic of Study Design:

2 BACKGROUND INFORMATION AND SCIENTIFIC RATIONALE

2.1 Background Information

Early childhood caries (ECC) is defined as dental caries in the primary teeth of children of the ages of 0-6 years.¹ Although ECC is largely preventable and the general prevalence of this common childhood infection is in decline, marked disparities exist.²⁻⁴ The disease levels seen in American Indian/Alaska Native (AI/AN) children reflect the most extreme disparities, suggesting the need for effective, culturally accepted interventions.⁵⁻⁷ Approaches that combine simple clinical procedures such as Fluoride Varnish (FV) with Oral Health Promotion (OHP) activities for children and parents/caregivers in a community-based setting appear to offer effective and efficient interventions in the prevention of ECC,⁸⁻¹³ yet professional personnel for delivery of these services are not always available. Consequently, alternative provider concepts, such as the use of dental therapists as extenders of the current dental care delivery system, are increasingly being explored, especially for use in geographically isolated communities.¹⁴⁻¹⁶ Although the effectiveness of some of these new strategies has not yet been fully demonstrated, there is evidence that health outcomes can be enhanced through interventions provided by trained paraprofessionals in community settings.¹⁷⁻²² This study will test innovative prevention services delivery programs and measure their effects on caries incidence in an AI preschool population.

The most recent Indian Health Service (IHS) report cites caries experience rates of 79% for AI/AN preschool children, with 68% having untreated dental decay, a prevalence more than 3 times greater than their non-Native counterparts^{5, 22} In Navajo Area, dental decay among preschool children is severe; with the mean number of decayed, missing and filled tooth surfaces (dmfs) for 2-5 year olds reaching 19.0 surfaces,²³ the highest in Indian Country. These data suggest that rates of dental decay experienced by AI/AN children today are the highest in the U.S., and perhaps the highest in the world.

While substantial evidence exists to document the poor oral health status of these children, there have been very few reports of intervention. Only Bruerd²⁰ has successfully demonstrated a community-based intervention to prevent ECC with AI/AN children. The project was funded from 1985-1990 to determine whether community-based health education could reduce the prevalence of decay among AI/AN children²¹. Twelve pilot Head Start (HS) sites received varying levels of OHP training and planned multidisciplinary educational interventions for individuals and communities. For the 12 sites, the average prevalence of decay in the post-program cohort was 25% less after 4 years; for the 5 sites that continued to implement the

program for 4 additional years, the difference was 38%.²⁰ The project did not deliver any direct clinical preventive services, and it did not have a controlled design.

Among the clinical interventions to prevent caries in children, the use of fluoride demonstrates the strongest evidence base and most predictable success.¹⁷ Professional and public health measures, including the use of fluoride mouth rinses, gels, dentifrices, and dietary supplements, are common means of preventing dental caries.¹ These measures are limited in scope, however, and benefit primarily those individuals who have financial means and access to regular professional oral health care services. FV is a professionally available topical agent that has been employed in the prevention of caries since 1964. It has been used extensively in European countries, and was approved by the FDA in 1991 as a cavity liner and desensitizing agent. Evidence from systematic studies of FV, while far more robust than for other professionally applied modalities, remains limited.¹⁸ Systematic reviews and meta analyses establish mean caries prevention at approximately 33% for primary teeth with the use of FV at 6-month intervals.^{9, 19, 23} These recent reviews, paired with the unique and favorable clinical characteristics of FV, have prompted the publication of clinical practice recommendations from the American Dental Association that support use of FV as the preferred technique for caries prevention therapy in children under the age of 6.¹⁸

Education programs attempt to increase knowledge, positive attitudes toward oral health care, and ensuing behaviors on the part of parents/caregivers about ECC and contributing factors. Parent education efforts may be aimed at influencing behaviors such as promoting dental visits, feeding, and/or oral hygiene practices. While parental educational attainment has an inverse relationship with ECC, knowledge alone appears to be insufficient to produce behavior change in children or adults. Systematic review of dental health education literature yields very few well-designed intervention studies and insufficient evidence for long term behavior change or significant reductions in caries incidence.²⁴

On the basis of treaties, the U.S. government has a trust responsibility to provide health care to members of federally recognized tribes—a duty filled by the IHS since 1955. IHS, however, provides care to only about 1.5 million out of 4.1 million who identify themselves as AI/AN, and is tremendously underfunded. This underfunding leads to very limited funding for dental health care within the IHS. Long waits for routine dental visits are common and specialty dental services are not provided.²⁵

Community-based health services have sometimes been delivered by specially trained paraprofessionals drawn from the community being served, with the implicit logic that members of a community are able to better communicate with patients and understand the barriers to care. In AI/AN communities, trained paraprofessionals known as Community Health Representatives (CHRs) have extended health care services for many years. While these paraprofessionals have worked successfully to educate clients in such areas as diabetes

control, smoking cessation, cardiovascular disease prevention, and medication compliance, their usefulness in promoting oral health has not been tested.

Head Start (HS) is a comprehensive child development program serving children ages 3-6 and their families. This community-based, child-focused program has an overarching goal of increasing the social competence of young children in low-income families. The HS Performance Standards mandate the program of services that grantee and delegate agencies must maintain; among these are standards supporting the provision of health, including oral health, education and services to children and families.²⁶

A pilot study of specially-trained Community Oral Health Specialists (COHS) administering FV and OHP in AI children on a Northern Plains reservation was developed and implemented in 2001-2005 by the initial Principal Investigator of this study, [name], to reduce ECC in AI children. The program was funded by a grant from HRSA Office of Rural Health Policy (HRSA 4 DIARH0003). The COHS completed a 160-hour training program that included orientation to health and oral health, science and prevention of dental caries, clinical procedures, and clinical activities related to screening, varnish application, and referrals. The program was based on home visits. The COHS completed 2,379 visits to 1,263 children. Among the children enrolled, about 83% received at least 1 COHS service and more than half received 2 or more standard doses of FV. An evaluation of the program was done using dental exams at baseline and follow-up, but the evaluation did not have sufficient statistical power to demonstrate efficacy of the intervention.

In summary, ECC is a major oral health problem among AI/AN children, and oral health funding for these children through the IHS is very limited. The investigators of this study will design an oral health intervention that has the potential of being cost-effective in the AI/AN community. Several elements will be combined together to create an oral health intervention that might reduce ECC in AI/AN children. These elements will include the use of specially trained COHS to administer FV and OHP in AI/AN children within HS programs. The program will also undergo a rigorous statistical evaluation.

2.2 Rationale

The hypothesis of this study is that an intensive intervention of specially trained COHS administering FV (offered 4x a year) and OHP for 2 years for AI children ages 3-6 in HSCs (Group 1) vs. the delivery of usual oral health care made available by the IHS Dental providers or other usual providers (Group 2) will reduce the dmfs increment in the Group 1 children when compared to the Group 2 children and show improved parent/caregiver dental knowledge, attitudes, and behaviors.

2.3 Potential Risks and Benefits

2.3.1 Potential Risks

Potential risks include disclosure of confidential information including oral health status, extent of oral disease, oral health knowledge, attitudes, and behaviors, and effect mediators or moderators. There is also the potential of psychological distress associated with the oral health screening and application of the FV with young children. Parents/caregivers and children will have the opportunity to terminate their involvement in the study at any time. Study staff will be trained in techniques to keep study data confidential. Patient identifying information will not be included in the research databases. Once data are collected, a research database will be created in which data are recorded using research ID numbers. All data will be stored on password-protected network drives, and paper copies of any data or consent forms will be kept in locked file cabinets.

Adverse reactions to the FV are extremely rare; particularly since dispensing of the FV and the single unit dosage delivered to each participant will be controlled. Adverse reactions may include temporary change in tooth color²⁷ or potential risk of contact allergy to the colophonium resin base if the varnish is applied to ulcerated gingival tissues. According to the FV package insert, edematous swelling has been reported only in rare instances, especially following application to extensive surfaces with FV. Though extremely rare, acute exacerbation of asthmatic conditions, or dyspnea, has occurred in asthmatic people. Nausea can occur in patients with known sensitive digestive systems, especially following extensive applications. More information is available from the FV MSDS form (*Appendix A*) attached. Intervention staff will be instructed to monitor children following fluoride application, recognize these adverse reactions and respond with prompt referral to the IHS dental clinic. After attending to urgent or emergent needs of the child, intervention staff will contact the study PI immediately to report the event and complete reporting requirements.

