6.2 Dosage, Preparation and Administration of Study Intervention/Investigational Product

Only trained study staff will apply the FV to the teeth of the children whose parents have consented. Aseptic procedures and universal precautions will be maintained at all times. Study records and HS child health records will document the application of the FV. Consistent with CDC Advisory Committee on Immunization Practices and standards of pediatric practice, COHSs will observe the child(ren) for a minimum of 15 minutes following the fluoride varnish

application to observe, resolve, and report any untoward effects. Parents will be provided with post-fluoride instructions each time the FV is administered.

Dosage guidelines include the following:

- a. 0.25 mL dosage for children with primary dentition only, or to treat any child requiring limited tooth surface or cavity area coverage
- b. 0.40 mL dosage for children with mixed dentition who require extensive tooth surface or cavity area coverage
- c. 0.50 mL dosage for children with permanent dentition who require extensive coverage.

Directions for administration are:

1. Treatment areas should minimally be “toothbrush” clean; a prophylaxis is not required.
2. Peel the foil pouch open to expose the VANISH unit-dose package and applicator brush.
3. Tear off the end of the unit-dose package and dispense the entire contents onto the dosing guide.
4. Use the applicator brush to thoroughly mix VANISH, since the components of all sodium fluoride varnishes can separate during storage. While mixing, keep the material evenly distributed inside the inner circle of the dosing guide.
5. Use the dosing guide to determine the amount of VANISH required.
6. For best results, excessive saliva is removed by blotting the tooth surfaces with gauze. Avoid passing applicator brush through pooled saliva to prevent premature setting on bristles.
7. Paint VANISH evenly to the areas being treated.
8. Consistent with CDC Advisory Committee on Immunization Practices and standards of pediatric practice, the COHSs will observe the child(ren) for a minimum of 15 minutes following the fluoride varnish application to observe, resolve, and report any untoward effects.

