7.3 Follow-up Visits for FV

The applications of FV for HS children and OHP will be delivered in the HSCs by the COHS (Group 1). FV will be offered 4x a year for 2 years to children in the classroom on the scheduled day; multiple attempts will be made to provide FV to children not in the classroom on the scheduled day. Group 2 participants will receive usual oral health care made available by the IHS Dental providers (or other dental providers outside the reservation).

Annual dmfs measure of the children, and parent ACASI survey to collect dental knowledge, attitudes, and behaviors will take place annually for 3 years. We will follow the families whose children age out of Head Start and make arrangements for them to complete the child oral health screening and parent ACASI survey at a convenient time and location. All annual follow-up assessments will be done as near as possible to the anniversary of the previous year's oral health screening at that HSC, with the goal of completing them within a month either side of that date.

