8.6 Type and Duration of Follow-up of Subjects after Adverse Events

Children who have a medically attended AE as defined in Sections 8.4.1-8.4.2 of the protocol will be followed weekly by the PI and/or study dentist until the AE resolves or stabilizes. This might include visits to the HSC or home visits by study staff. If the AE does not resolve within one month, the child will be referred to their usual medical or dental care provider as appropriate. If the need is/becomes urgent, immediate referral will be made.

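### Section 2.3.1 sends every listed varnish reaction, including acute asthma or dyspnea, to the IHS dental clinic, and no section names an emergency medical route

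*Combined protocol and SAP*

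**What the plan says.** Section 2.3.1 names temporary tooth color change, contact allergy to the resin base, edematous swelling, asthma exacerbation or dyspnea, and nausea. On swelling it says that "edematous swelling has been reported only in rare instances". On breathing it says that, though extremely rarely, "acute exacerbation of asthmatic conditions, or dyspnea, has occurred in asthmatic people". The instruction that follows covers the whole list: staff are to "recognize these adverse reactions and respond with prompt referral to the IHS dental clinic". The next sentence reads "After attending to urgent or emergent needs of the child, intervention staff will contact the study PI immediately to report the event".

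Three other sections bear on the response:

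- Section 6.2 has the Community Oral Health Specialists (COHS) watch each child for at least 15 minutes after application "to observe, resolve, and report any untoward effects".
- Section 7.3 fixes the place and the people: "The applications of FV for HS children and OHP will be delivered in the HSCs by the COHS".
- Section 8.6 says that if an event has not resolved within a month, "the child will be referred to their usual medical or dental care provider as appropriate". It adds: "If the need is/becomes urgent, immediate referral will be made".

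Sections 2.3.2 and 8.4.3 mention that the Head Start teacher has procedures for medical emergencies. Both do so for a dental emergency found in a child, with an abscess as the example.

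**The concern.** The instruction is written for the people who apply the varnish. Section 3.1.1.1 describes the COHS as specially trained community paraprofessionals, and they work in Head Start classrooms with children aged 3 to 6. An acute asthma attack or dyspnea in a child of that age needs medical care first, and swelling may need it too, depending on its site. The rule as written gives these staff one named place to send the child, and it is a dental clinic.

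The children at risk are not kept out of the trial. Section 5.2 excludes Group 1 children with a known allergy to a varnish component or with chronically irritated oral mucosa. It does not name asthma, and criterion C leaves other conditions to the investigator's judgment. A child with asthma, the group that 2.3.1 itself singles out for breathing reactions, can therefore receive varnish.

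At stake is the safety of a child during or shortly after an application. No endpoint, estimate or analysis is affected.

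**Working it through.** The plan states no figure on this point and no arithmetic applies. The check is whether any section gives staff a medical route for an acute reaction to varnish.

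1. **Section 2.3.1, referral sentence.** It applies to all the reactions just listed. It names one destination, the IHS dental clinic, and makes no distinction by severity.
2. **Section 2.3.1, next sentence.** It puts the child's urgent or emergent needs ahead of the call to the PI. It sets a priority, but names no provider and no procedure.
3. **Section 6.2.** It requires observation for at least 15 minutes and expects the COHS to resolve what they see. It gives no means and no point at which to call for medical help.
4. **Section 8.6.** It applies to children who have a medically attended adverse event, so care has already been reached. It provides weekly follow-up, then the usual medical or dental provider if the event is unresolved at one month, and immediate referral if the need is or becomes urgent. The urgent destination is not stated. This is follow-up of a known event and not first response in the classroom.
5. **Sections 7.4, 8.4.1 and 8.4.2.** The safety contact asks about urgent or emergent care visits, the adverse event definition includes anaphylaxis, and the serious event definition uses anaphylaxis as its example of a life-threatening event. The plan thus treats severe acute reactions as possible. These are rules for capture, grading and reporting, and none says what staff should do at the time.
6. **Sections 2.3.2 and 8.4.3.** Medical-emergency procedures exist at the Head Start centers, but the protocol calls on them only for a dental emergency.

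Items 1 and 6 together show the problem most clearly. As written, a child with a dental abscess is directed to the center's medical-emergency procedures, while a child with dyspnea after varnish is directed to a dental clinic.

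Items 2, 3 and 4 do contain general urgent-care wording. None of the six names emergency services, an emergency department or on-site emergency treatment for a varnish reaction.

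**The case against.** The strongest reply is that the sections, read together, already protect the child. Staff observe after each application, attend to emergent needs before reporting, and work in centers where a teacher has medical-emergency procedures. Nothing says those procedures are unavailable for a varnish reaction. Section 2.3.1 is also a risk statement and not an operating manual. Section 4 assigns operations to the Manual of Procedures (MOP), and Section 13.2 sends the COHS curriculum to the review boards. Either may hold a full emergency route, and neither is among the documents reviewed.

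Much of this stands. A reader might infer that the protocol denies emergency care, or that the trial has no emergency procedure. The documents do not support either reading: the general urgent-care wording is there, and what the unseen materials contain cannot be asserted.

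A reader might also want to count how many of the listed reactions belong outside a dental clinic. That is a clinical judgment and not something the text settles. Edematous swelling is linked to application over extensive surfaces and is not said to involve the face or airway, and asthma exacerbation and dyspnea can be read as one item. Nor do the documents describe what the IHS dental clinic or its facility can provide.

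What the reply does not remove is the sentence itself. It does more than omit detail: it states a rule, and the rule names an unsuitable destination for an acute breathing reaction. Because Section 4 describes the MOP as turning the protocol into a working guideline, the protocol sentence should not point the wrong way.

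**Conclusion.** The point holds in this limited form. Section 2.3.1 gives a single dental destination for reactions that include acute asthma exacerbation or dyspnea, and no section of the protocol names an emergency medical destination or first-response procedure for acute respiratory or systemic allergic reactions.

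It is a low-probability safety correction. The only frequency information is that such reactions are rare or extremely rare, so no expected number of events can be given. The number of planned varnish applications would not supply one either, because it measures exposure and not harm.

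The conclusion rests on one clinical assumption, that an acute breathing reaction in a preschool child needs medical care before dental care, and on the protocol text alone. If the MOP or the COHS curriculum already has a route, the remaining defect is a mismatch between that route and 2.3.1. It ranks as a cheap improvement.

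**What to change.** Replace the referral sentence in 2.3.1 with two, split by severity:

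- Respiratory signs, facial or airway swelling, or other systemic allergic signs: start the Head Start medical-emergency procedures and obtain emergency medical care at once.
- Local or mild reactions, such as tooth color change or a local contact reaction: refer promptly to the IHS dental clinic.

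The clinical team should decide where nausea belongs. It should also confirm that the Head Start procedures cover an acute reaction to varnish, since the protocol does not describe their content. Add a cross-reference from 6.2 to this route, and include it in COHS training. If the MOP already has such a procedure, align the 2.3.1 sentence with it and cite it.

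The cost is one reworded sentence, one cross-reference and one training item. Sample size, visits, data collection and analysis do not change.
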